1 INTRODUCTION

1.1 Background

Atherosclerotic cardiovascular disease (ASCVD) is the leading cause of death and accounts for 41% of all cause death in China[1]. Management of dyslipidemia is the main strategy to reduce the risk of ASCVD. To lower lipids, statins should be the first-line treatment in clinical practice. However, patients on statin treatment have been shown to exhibit an increased risk of dys-glycaemia and development of type 2 diabetes mellitus (T2DM)[2].

Dyslipidemia and diabetes mellitus are major risk factors of ASCVD, and the prevalence has been reached 40.4%[3] and 10.9%[4] among Chinese adults. China has the largest number of diabetes mellitus with 109.6 million Chinese adults suffering from the disease[5]. Genetic susceptibility may play an important role as Asians have a 60% increased risk of diabetes compared with Caucasians after adjusting for age, sex, and BMI[6].

Therefore, the management of patients with dyslipidemia in Prediabetes poses a challenging dilemma that requires balancing the benefit of reducing serum cholesterol against the risk of dys-glycaemia and development of T2DM, especially for Chinese even Asians.

Xuezhikang (XZK), a traditional Chinese medicine that contains natural lovastatin and multiple components for hyperlipidemia treatment, may have a lower risk of incident diabetes compared with the statin cohort. However, limited information was available to demonstrate XZK does not adversely affect glucose metabolism or incident diabetes. Therefore, we hypothesize that XZK 1200mg/d, compared to atorvastatin 20mg/d, has a favorable impact on the HbA1c levels in dyslipidemia patients with Prediabetes .

The Xtreme study is a 24-week, multi-center, randomized, open-label clinical trial that will compare the impact of XZK and Atorvastatin on glucose metabolism in dyslipidemia patients with Prediabetes. Prediabetes, including impaired fasting glucose (IFG), impaired glucose tolerance (IGT), or A1C 5.7–6.4% . Recruitment will occur at approximately 20 centers, where 392 adult participants in Prediabetes with dyslipidemia will be randomly assigned to receive XZK 1200mg/d or Atorvastatin 20mg/d. Randomized participants will be followed to a common study period.

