In addition, XZK has been proved to contain multiple active ingredients which leads to unique MOA and multiple benefits[13]. It is composed of 13 kinds of natural statins, unsaturated fatty acids, ergosterol, amino acids, flavonoids, alkaloid, trace elements, and other substances, and thus could be regarded as a natural lipid lowering polypill[14]. All the above-mentioned components might be involved in the mechanism of XZK to multiple benefits such as antiatherosclerosis, liver protection, anticancer, neural regulation and protection, and kidney protection effects[13]. Previous animal and cell experiments have shown that XZK can also activate the PPAR α pathway and up-regulate apolipoprotein A5 (apolipoprotein A5 is the key regulator of TG metabolism) to achieve higher TG reduction when it reduces LDL-C by the same extent as simvastatin[18]. It is speculated that non-statin elements within XZK may play a synergistic role in regulating blood lipids and inhibiting the synthesis of triglycerides. The China Coronary Secondary Prevention Study (CCSPS) and other clinical studies confirmed that XZK capsules reduce lipid and significantly reduce the overall mortality of patients with coronary heart disease, the incidence of cardiovascular events. According to Chinese guidelines for the management of dyslipidemia in adults of 2016 revision, XZK amongst other statins are recommended for the first-line treatment of cholesterol controlling. Meanwhile, XZK 1200mg/d and Atorvastatin 20mg/d are medium intensity statins recommended in guideline[3]. therefore, we choose Atorvastatin 20mg/d as control drug in our research.

Physicians faced with a dyslipidemia patient with prediabetes often use statins therapy due to perceived efficacy. However, XZK is a promising option in this patient group due to their significantly lower risk of dys-glycaemia without compromising efficacy for lowering lipids in hyperlipidemia. Establishing comparable recurrent NODM rates in individuals with previous Prediabetes state would result in superior DM prevention for these patients.

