5 STUDY ASSESSMENTS

5.1 Efficacy Assessments

5.1.1 Primary endpoint

The change value of HbA1c levels from baseline to 24 Weeks or before antidiabetic therapy initiation within 24 weeks.

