5.1.2 Secondary endpoints

The change value of FBG, PPG 2h and HOMA-IR from baseline to 24 Weeks or before antidiabetic therapy initiation within 24 weeks.

The percentage change of LDL-C levels from baseline to 24 Weeks or before antidiabetic therapy initiation within 24 weeks.

The percentage change of non HDL-C levels from baseline to 24 Weeks or before antidiabetic therapy initiation within 24 weeks.

The change value of HbA1c levels from baseline to 12 Weeks or before antidiabetic therapy initiation within 12 weeks.

The change value of FBG, PPG 2h and HOMA-IR from baseline to 12 Weeks or before antidiabetic therapy initiation within 12 weeks.

The percentage change of LDL-C levels from baseline to 12 weeks or before antidiabetic therapy initiation within 12 weeks.

The percentage change of non HDL-C levels from baseline to 24 Weeks or before antidiabetic therapy initiation within 12 weeks.

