5.2 Safety Assessments

5.2.1 Clinical Assessment

Baseline clinical and demographic characteristics will be measured at study enrollment. Variables of interest will include gender, age, weight, height, waistline, medical history, family history, smoking status, alcohol intake.

Physical examination:

Blood pressure, heart rate and ECG are measures of various physiological statistics, in order to assess the most basic body functions. Vital signs are also an essential part of a case when the subjects appear SAEs. The act of taking vital signs normally entails recording pulse rate (or heart rate) and blood pressure , but may also include other measurements.

New onset medical conditions:

ASCVD, hypertension, cancer, etc.

5.2.2 Laboratory assessments:

Blood samples for determination of clinical chemistry and urinalysis will be taken at the times indicated in the Study Plan and Time Schedule (see table 1).

The following laboratory efficacy variables will be measured:

Serum lipids (TG/non HDL-C/TC/LDL-C), HbA1c (%), Plasma Glucose (PG), insulin, C-peptide levels at fasting and 2 h after drinking glucose solution(75g glucose)

The following laboratory safety variables will be measured:

Hepatic function (Bilirubin, albumin, liver enzymes), Creatine kinase (CK), Renal function (Serum creatinine, BUN ,eGFR), Routine blood test, Pregnancy test (HCG test for women of childbearing potential only)

Notes: Male eGFR= $170 \times (\text{Scr})^{-1.234} \times (\text{Age})^{-0.179}$

Female eGFR= $170 \times (\text{Scr})^{-1.234} \times (\text{Age})^{-0.179} \times 0.79$

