6.1.1 Adverse Events

An adverse event is defined as any untoward medical occurrence in a clinical trial subject. The event does not necessarily have a causal relationship with study treatment. The investigator is responsible for ensuring that any adverse events observed by the investigator or reported by the subject are recorded in the subject' s medical record.

The definition of adverse events includes worsening of a pre-existing medical condition. Worsening indicates the pre-existing medical condition has increased in severity, frequency, and/or duration, and/or has an association with a significantly worse outcome. A pre-existing condition that has not worsened during the study, and involves an intervention such as elective cosmetic surgery or a medical procedure while on study is not considered an adverse event.

Overdose should also be considered as an AE.

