6.9 Adverse events based on examinations and tests

Deterioration as compared to baseline in protocol-mandated including laboratory values, vital signs should therefore only be reported as AEs if they fulfil any of the SAE criteria or are the reason for discontinuation of treatment with the investigational product.

If deterioration in a laboratory value/vital sign is associated with clinical signs and symptoms, the sign or symptom will be reported as an AE and the associated laboratory result/vital sign will be considered as additional information. Wherever possible the reporting Investigator uses the clinical, rather than the laboratory term (e.g., anaemia versus low haemoglobin value). In the absence of clinical signs or symptoms, clinically relevant deteriorations in non-mandated parameters should be reported as AE(s). Deterioration of a laboratory value, which is unequivocally due to disease progression, should not be reported as an AE/SAE. Any new or aggravated clinically relevant abnormal medical finding at a physical examination as compared with the baseline assessment will be reported as an AE.

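### New-onset diabetes motivates the trial but is not a prespecified outcome, and the laboratory rule in section 6.9 would leave most asymptomatic conversions out of the adverse event tables

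*Protocol*

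**What the plan says.** **Motivation.** Protocol section 1.1 describes the clinical problem as "balancing the benefit of reducing serum cholesterol against the risk of dys-glycaemia and development of T2DM". Section 1.2 chooses prediabetes because it raises the risk of diabetes, cites a cohort hazard ratio of 0.46 for incident diabetes with red yeast rice against lovastatin, and closes with "Establishing comparable recurrent NODM rates in individuals with previous Prediabetes state would result in superior DM prevention for these patients".

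**Endpoints.** The primary endpoint (5.1.1) is "The change value of HbA1c levels from baseline to 24 Weeks or before antidiabetic therapy initiation within 24 weeks". The glycaemic secondary endpoints (5.1.2) have the same form, for example "The change value of FBG, PPG 2h and HOMA-IR from baseline to 24 Weeks or before antidiabetic therapy initiation within 24 weeks", with week-12 versions. None is a count of participants who become diabetic.

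**Safety.** The new-onset conditions in 5.2.1 are "ASCVD, hypertension, cancer, etc". The list of events needing additional data in 6.3 does not include diabetes. Section 6.9 says that deteriorations in protocol-mandated laboratory values "should therefore only be reported as AEs if they fulfil any of the SAE criteria or are the reason for discontinuation of treatment", and later "Deterioration of a laboratory value, which is unequivocally due to disease progression, should not be reported as an AE/SAE". Section 6.1.1, by contrast, states "The definition of adverse events includes worsening of a pre-existing medical condition", and section 6.8 prefers a diagnosis to a list of signs and symptoms.

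**Data collected.** Table 1 schedules fasting and 2-hour glucose at weeks 0, 4, 12 and 24, and HbA1c at weeks 0, 12 and 24. Diabetes thresholds are written in Exclusion 2 (section 3.2). Section 7.7.2 has all treatments recorded in the CRF.

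**The concern.** The endpoint wording allows for participants who start antidiabetic therapy within the 24 weeks, so the protocol expects some conversions, but nothing in it counts them. The natural fallback is adverse event reporting, and section 6.9 narrows that route for exactly the tests that would detect conversion.

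Two things are at stake. First, a difference in mean HbA1c does not say how many people crossed into diabetes: a small mean shift is compatible with more, fewer or equal conversions. Second, an adverse event table with few diabetes cases in either arm could be read as reassurance when it mainly reflects the reporting rule. Treatment is open-label and the stated hypothesis favours Xuezhikang, so discretionary recording could also differ by arm.

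**Working it through.** **Step 1. Follow one participant through the rules.** Take an illustrative participant without symptoms who goes from HbA1c 6.2% at baseline to 6.7% at week 12, with FPG 7.3 mmol/L.

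- Exclusion 2: 6.7% ≥ 6.5% and 7.3 ≥ 7.0 mmol/L, so two laboratory criteria for diabetes are met.
- 5.1.2: the values enter the week-12 means for HbA1c and fasting glucose. The person is not counted as a case.
- 6.9, rule on protocol-mandated values: HbA1c and glucose are mandated by Table 1. If the event is not serious and study drug continues, it is not an adverse event.
- 6.9, disease-progression sentence: may exclude it as well, but only if progression is unequivocal; the protocol does not say whether prediabetes to diabetes qualifies.
- 6.1.1: worsening of a pre-existing condition, so it is an adverse event.
- 6.8: a diagnosis of diabetes could be recorded as such.
- 6.2: recorded if the investigator regards it as of particular concern.

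The same participant is reportable under 6.1.1 and not under 6.9, and the protocol does not say which prevails.

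**Step 2. Analysis population.** Section 8.3 defines the FAS, used for efficacy and safety, by a non-missing week-24 HbA1c. If this participant dropped out after week 12, the case would be lost from any count based on the FAS.

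**Step 3. The plan's own sample size (8.1).** Inputs: difference 0.3, SD 1.0, alpha 5%, power 80%. Normal approximation, two-sided: n = 2(1.960 + 0.842)² × 1.0² / 0.3² = 174.4, so 175 per arm; the t-test version gives 175.4, so 176. With 10% dropout, 176/0.9 = 195.6, so 196 per arm and 392 in total. The stated figures reproduce and are unaffected by this point.

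**Step 4. What a diabetes count could show.** The protocol gives no 24-week risk, so the atorvastatin risk p is assumed over a range. Xuezhikang risk: q = 1 − (1 − p)^0.46, using the hazard ratio cited in section 1.2. n = 176 per arm.

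- 95% half-width of the risk difference = 1.96 × √[p(1−p)/176 + q(1−q)/176]
- Power = Φ{[(p − q) − 1.96·SE₀]/SE₁}, where SE₀ uses the pooled risk and SE₁ is the unpooled standard error above.

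| Assumed p | q | Expected cases (atorvastatin / Xuezhikang) | Risk difference, points | 95% half-width, points | Power |
|---|---|---|---|---|---|
| 2% | 0.9% | 3.5 / 1.6 | 1.1 | 2.5 | 13% |
| 5% | 2.3% | 8.8 / 4.1 | 2.7 | 3.9 | 26% |
| 10% | 4.7% | 17.6 / 8.3 | 5.3 | 5.4 | 47% |
| 20% | 9.8% | 35.2 / 17.2 | 10.2 | 7.4 | 77% |

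At p = 10%, 385 per arm would be needed for 80% power. Over 2% to 10% the total is about 5 (3.5 + 1.6) to 26 (17.6 + 8.3) cases.

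**The case against.** The strongest reply is that nothing in the planned analysis is invalid. The title and objectives concern glucose metabolism and HbA1c; the sentence on new-onset diabetes rates is background, not an objective. Incidence is underpowered at 24 weeks, so a continuous primary endpoint is a sound choice. A threshold table from scheduled laboratory data may also sit in an analysis plan that is not shown. The endpoint choice stands. What remains is that the rule in 6.9 governs what sites record, which an analysis plan cannot repair afterwards, and that it conflicts with 6.1.1 and 6.8.

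A reader might infer more than the protocol supports:

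- *That the trial cannot report incident diabetes by arm.* It can. The tests are efficacy data in both arms whatever the adverse event rules say, the thresholds are in Exclusion 2, and antidiabetic starts are recorded.
- *That a converter vanishes from the efficacy results, or is muted by the rule on antidiabetic therapy.* The values enter the means, and taking the value before therapy keeps the rise; a value lowered by treatment is what would mute it.
- *That the disease-progression sentence by itself bars diabetes from reporting.* Unequivocal progression is hard to establish in a trial asking whether the drug causes dysglycaemia. The rule on protocol-mandated values is the operative one.
- *That diabetes is deliberately left off the list in 5.2.1.* That list is open-ended.

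One criticism of the remedy also stands. Counting any single threshold crossing among eight post-baseline tests (three FPG, three 2-hour glucose, two HbA1c), in people who may enter just below the cut-offs, will pick up measurement variability. The fix has to allow for that.

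**Conclusion.** The point holds as one of prespecification and recording. The harm that motivates the trial has no defined outcome in the protocol. Adverse event counts of it would be incomplete and site-dependent because 6.9 conflicts with 6.1.1 and 6.8. A derived count would be post hoc as far as the protocol states, and on the FAS it would lose early converters without a week-24 HbA1c.

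The size depends on a conversion risk that the protocol does not give. The table also assumes that the cited observational hazard ratio, which is against lovastatin, carries over to atorvastatin. Under the assumed risks of 2% to 10% the confidence interval half-width (2.5 to 5.4 points) exceeds the expected difference (1.1 to 5.3 points) throughout. The outcome can therefore only be descriptive. That supports HbA1c change as primary and leaves 392 unaffected. This should be corrected, but it does not threaten the primary analysis.

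**What to change.** 1. Add to 5.1.2 a descriptive secondary or safety outcome: participants who after baseline meet a laboratory criterion in Exclusion 2 (FPG or 2-hour glucose at weeks 4, 12 or 24; HbA1c at weeks 12 or 24) or start antidiabetic therapy. Report it by arm with risk difference and 95% CI.
2. Count it in all randomised participants with any post-baseline glycaemic test or a recorded antidiabetic start, not in the FAS.
3. Show separately those who cross a threshold on one test only and those who cross on more than one test or start treatment.
4. Name new-onset diabetes in 5.2.1, and reconcile 6.9 with 6.1.1 and 6.8 so that sites have one recording rule.
5. Label the outcome descriptive. A laboratory-based count also uses assessments that section 3.3.3 says are performed blinded, which limits the influence of open-label recording.

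Cost: protocol wording and one extra table. No new visit, test or participant is needed. The downsides are few events, one more comparison, and some single unconfirmed threshold crossings, which item 3 makes visible.

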7 INVESTIGATIONAL PRODUCT AND OTHER TREATMENTS

7.1 Investigational product

	Investigational product	Dosage form and strength	Manufacturer
Experimental drug	Xuezhikang Capsule	300mg capsule	WBL Peking University Biotech Co
Control drug	Atorvastatin Calcium Tablets	20mg tablet	Pfizer Inc

7.2 Dose and treatment regimens

Experimental group: Xuezhikang Capsule, 1200mg / day, twice a day, 2 capsules each time, after meals in the morning and evening;

Control group: Atorvastatin Calcium Tablets, 20mg/day, once a day, one tablet each time, before bedtime;

Patients should start the treatment after the day of randomization, and Continuous treatment for 24 weeks.

7.3 Labelling

The packaging label of each drug will include at least the following information: name of Sponsor, Investigational product/study drug dosage form, route of administration, and quantity of dosage units, study code, medication instructions, expiration date, "for clinical trial use only", batch number, storage conditions, and " keep out of reach of children ".

7.4 Storage

Only participants enrolled in the study may receive study drug and only authorized site staff may supply or administer study drug. All study drugs must be stored in a secure, environmentally controlled, and monitored (manual or automated) area in accordance with the labeled storage conditions with access limited to the investigator and authorized site staff. The investigator, institution, or the head of the medical institution (where applicable) is responsible for study drug accountability, reconciliation, and record maintenance (i.e., receipt, reconciliation, and final disposition records).

7.5 Compliance

Participants in both arms will self-administer the study the study drug at home, compliance with study intervention will be assessed at each visit. Compliance will be assessed by counting returned tablets and patient diary during the site visits and documented in the source documents and CRF.

7.6 Accountability

The study drug provided for this study will be used only as directed in the study protocol.

The study personnel will account for all study drugs dispensed to and returned from the subject.

Study site personnel, if applicable, or the monitor will account for all received study drugs and return all unused study drugs to sponsor.

Certificates of delivery and return should be signed.

7.7 Concomitant and other treatments

7.7.1 Prohibited combination treatment

Any drug that may affect glucose metabolism, such as metformin , steroids, etc.

7.7.2 Permitted combination treatment

In addition to the drugs listed above, other drugs are permitted to combine therapy, and the Investigators determine whether it is necessary to give patients a stable dose of combination treatment if possible.

Any treatment performed during the study should be recorded in the CRF.

8 STATISTICAL ANALYSES

8.1 Sample size estimate

The primary endpoint of the study is the change value of HbA1c levels from baseline to 24 Weeks or before antidiabetic therapy initiation within 24 weeks.

We assume that the HbA1c level doesn't change in XZK group, and an increase of HbA1c level by 0.3% in atorvastatin 20mg group based on findings from Koh K et al. The SD of change of HbA1c level is 1.0% for both treatment.

The sample size of each group of 176 will provide 80% power at a 5% significance level. Considering 10% drop out rate, the total sample size is 392.

8.2 General consideration

Analyses will be performed by SAS 9.4 statistical software. Descriptive statistics will be calculated, including n, means, standard deviations, medians, and interquartile ranges for continuous variables and frequency counts and percentages for categorical variables. Percentage will be calculated based on non-missing data unless otherwise specified. Data will be examined for skewness, outliers. Transformations will be undertaken as needed.

Missing data will be assumed missing at random or missing completely at random. In general, no imputation will be applied unless otherwise specified.

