- (9) Other endocrine diseases that might influence the levels of lipid or lipoprotein, such as hypothyroidism.
- (10) Patient has participated in clinical trials of other drugs in the past three months.
- (11) Previous statin treatment causes creatine kinase (CK) increased 10 times, or myalgia myopathy (muscle pain or muscle weakness, accompanied by

	
Creatine phosphokinase (CK) exceeds 10 times the ULN)
 
(12)Estimated life expectancy < 6 months at the time of enrollment
 
(13)Abuse of alcohol, or history of alcohol abuse.
 
(14)Close affiliation with the investigators, e.g., a close relative for the investigator, dependent person (e.g., employee or student of the investigators)

Visit plan	5 visits: including enrollment period, baseline period, 4 weeks, 12 weeks and 24 weeks after randomization
Statistical Analyses	
Analyses will be performed by SAS 9.4 statistical software.
 
Descriptive statistics will be calculated, including n, means, standard deviations, medians, and interquartile ranges for continuous variables and frequency counts and percentages for categorical variables.
 
Percentage will be calculated based on non-missing data unless otherwise specified. Data will be examined for skewness, outliers.
 
Transformations will be undertaken as needed.
 
Missing data will be assumed missing completely at random. In general, no imputation will be applied unless otherwise specified. The primary and secondary endpoint will be analyzed using covariance(ANCOVA) model with treatment (XZK, atorvastatin) use the baseline HbA1c as the covariate.

Data collection	Case report form (CRF)

TABLE OF CONTENTS

STUDY PROTOCOL SUMMARY..... 2

TABLE OF CONTENTS 6

LIST OF ABBREVIATIONS AND DEFINITION OF TERMS..... 11

1 INTRODUCTION..... 13

1.1 Background 13

1.2 Rationale for study design 13

1.3 Benefit/risk and ethical assessment 15

1.4 Study Design 17

 1.4.1 Overall design 17

 1.4.2. Randomization 17

 1.4.3. Minimizing Sources of Bias 17

 1.4.4 Number of Centers 17

 1.4.5 Number of Participants..... 17

 1.4.6 Estimated Study Duration 17

 1.4.7 Study Duration for Participants..... 18

 1.4.8 End of Study..... 18

2 STUDY OBJECTIVES 18

2.1 Primary Objective 18

2.2 Secondary Objective 18

2.3 Safety 19

3 STUDY POPULATION 19

3.1 Inclusion Criteria..... 19

3.2 Exclusion Criteria..... 20

3.3 Subject enrolment and randomization 21

3.3.1 Number of Centers	21
3.3.2 Number of Participants.....	21

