8.4 Efficacy analysis

8.4.1 The primary endpoints

The change value of HbA1c levels from baseline to 24 Weeks or before antidiabetic therapy initiation within 24 weeks will be analyzed using covariance(ANCOVA) model use the treatment group(XZK, atorvastatin) as the group and the baseline HbA1c as the covariate. The results will be presented as least squares means (lsmeans) with 95% confidence intervals and p-values. Model assumptions will be explored and, if necessary, appropriate transformations or non-parametric analysis techniques will be used. The primary analysis set for this analysis is the full analysis set (FAS).

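### The summary (MCAR) and section 8.2 (MAR or MCAR) disagree, and the planned primary analysis is valid only if missingness depends on nothing beyond arm and baseline HbA1c

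*Protocol*

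**What the plan says.** - Protocol summary, Statistical Analyses: "Missing data will be assumed missing completely at random".
- Section 8.2: "Missing data will be assumed missing at random or missing completely at random. In general, no imputation will be applied unless otherwise specified".
- Section 8.3: the full analysis set (FAS) admits only treated, randomized participants whose week-24 HbA1c is available.
- Section 8.4.1: the primary model is an ANCOVA, to "use the treatment group(XZK, atorvastatin) as the group and the baseline HbA1c as the covariate", run in the FAS.
- Table 1 and section 4.2.2: HbA1c is scheduled at weeks 0, 12 and 24 for everyone, and fasting and 2-hour glucose also at week 4.
- Section 5.1.2 uses the week-12 value as a separate secondary endpoint: "The change value of HbA1c levels from baseline to 12 Weeks or before antidiabetic therapy initiation within 12 weeks".
- Section 3.8 asks that HbA1c be collected to the end of the study, also after study drug is stopped.

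**The concern.** The two statements of the missing-data assumption differ, and the wider one does not fit the analysis. Under MAR in its usual sense, the chance of a missing week-24 value may depend on anything observed, including week-12 HbA1c and glucose at weeks 4 and 12. An ANCOVA that conditions only on arm and baseline HbA1c, with incomplete participants removed, is not protected against that. Removal is fixed twice: 8.3 excludes these participants from the FAS, and 8.4.1 without imputation would delete them even from a wider set.

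Treatment is open-label. The laboratory and outcome assessors are blinded to allocation (1.4.3, 3.3.3), but the protocol does not say that interim HbA1c or glucose results are withheld from patients or sites. Dropout that responds to those results, and does so differently by arm, is therefore conceivable. At stake is the primary between-arm difference, which could be pulled towards or away from zero depending on which arm loses its higher values. The information that would correct this for dropout after week 12 will already be in the database.

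**Working it through.** **Inputs from section 8.1.** The planned difference is 0.3% (HbA1c unchanged on XZK, a 0.3% rise on atorvastatin), and the change is given an SD of 1.0% in each arm. The stated result is: "The sample size of each group of 176 will provide 80% power at a 5% significance level". An allowance for 10% dropout brings the total to 392.

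**The plan's own figure.** n per arm = 2(1.96 + 0.8416)² × 1.0² / 0.3² = 174.4, so 175 by the normal approximation. The t-test gives 175.4, so 176. Inflation: 176/0.9 = 195.6, so 196 per arm and 392 in total. The figures reproduce with a two-sided test.

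**Assumptions the protocol does not give.**
- Week-12 and week-24 changes are bivariate normal, SD 1.0 each, with an arm difference of 0.3 at both times.
- Their correlation ρ is 0.5 to 0.8.
- Change is unrelated to baseline HbA1c.
- All dropout is after week 12, with logit P(drop) = a + b × (week-12 change). The slope b is 0.5 to 1 per 1% HbA1c, and a is set to give the stated dropout rate.

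**Formula.** Let m be the mean of (week-12 change minus its arm mean) among those who stay in an arm. The mean week-24 change of the stayers is the true mean plus ρm, so

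complete-case difference = 0.3 + ρ(m_ATV − m_XZK).

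Power = Φ(difference / √(2/176) − 1.96), with √(2/176) = 0.1066. The values of m come from numerical integration.

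| Dropout scenario | b | m_XZK | m_ATV | Difference, ρ = 0.5 to 0.8 | Loss | Power |
|---|---|---|---|---|---|---|
| MCAR, or equal rate and slope in both arms | 0 to 1 | equal | equal | 0.300 | 0% | 80% |
| One common rule, 10% overall (9.3% v 10.7%) | 0.5 | −0.0457 | −0.0520 | 0.297 to 0.295 | 1.1% to 1.7% | 80% to 79% |
| One common rule, 10% overall (8.8% v 11.2%) | 1 | −0.0803 | −0.1011 | 0.290 to 0.283 | 3.5% to 5.5% | 78% to 76% |
| Depends on HbA1c in atorvastatin arm only, 10% each | 0.5 | 0 | −0.0488 | 0.276 to 0.261 | 8% to 13% | 73% to 69% |
| Same, 10% each | 1 | 0 | −0.0908 | 0.255 to 0.227 | 15% to 24% | 67% to 57% |
| Same slope in both arms, 5% XZK v 15% atorvastatin | 1 | −0.0471 | −0.1326 | 0.257 to 0.232 | 14% to 23% | 67% to 58% |
| Atorvastatin arm only, 5% v 15% | 1 | 0 | −0.1326 | 0.234 to 0.194 | 22% to 35% | 59% to 44% |

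Last row at ρ = 0.8: 0.3 + 0.8 × (−0.1326) = 0.194. The loss is 0.106/0.3 = 35%, and power is Φ(0.194/0.1066 − 1.96) = Φ(−0.14) = 44%. Simulating whole trials gives the same picture, with power from about 44% to 74% over the arm-specific rows.

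**With week 12 used.** In simulation, an estimate that carries the dropouts through their week-12 HbA1c returned 0.30 in every one of these MAR settings, within simulation error. Under MCAR its standard error was about 1% to 4% smaller than that of the complete-case analysis, so using week 12 costs no precision.

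**Timing.** If half the dropout comes before week 12 and is unrelated to HbA1c, the bias in the atorvastatin-only rows at 10% per arm roughly halves, to 0.014 to 0.038.

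**The case against.** - **The large figures need arm-specific dropout.** A reader might infer that the primary difference will shrink by up to a third because patients with rising HbA1c leave and more of them are on atorvastatin. That describes one common rule in both arms, which costs only 1% to 6%. The protocol does not state that rates or rules differ by arm; the open-label design only makes it plausible. This objection stands.
- **Patients with raised HbA1c need not leave.** Section 3.7.1 lists no HbA1c threshold for stopping drug. Sections 3.7.1, 3.7.3 and 3.8 keep participants in follow-up after stopping. The documents do not show that such patients are the ones most likely to be missing. This also stands.
- **Week 12 is not ignored for everyone.** A reader might infer that it is. Under 5.1.1 the endpoint for someone who starts antidiabetic therapy is the value before it, which may be the week-12 value. However, the FAS in 8.3 still demands a week-24 value from that person, so the two sections do not fit.
- **Dropout before week 12.** There is then no post-baseline HbA1c, and informative early dropout is not corrected. This stands as a limit on the remedy.
- **MAR could be read narrowly,** as conditional on arm and baseline HbA1c only, and the analysis would then fit. Section 8.2 does not say so, and the summary says something different again.
- **Imputation and sensitivity analyses may be in an unseen SAP.** Their absence is not the point here. The protocol itself fixes the assumption, the analysis set and the model, and these do not agree.

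**Conclusion.** The concern holds in this limited form. The summary and 8.2 state different assumptions, and the analysis fixed by 8.3 and 8.4.1 is not valid under the general MAR that 8.2 allows. The consequence is a possible bias, not a demonstrated one. It is about nil under MCAR or with equal dropout rates and rules, and about 1% to 6% of the 0.3% difference under one common rule at 10% overall. It reaches about 8% to 35%, with power about 44% to 74%, only if dropout rates or their dependence on HbA1c differ by arm. All of this rests on assumed slopes of 0.5 to 1 per 1% HbA1c, an assumed week-12/week-24 correlation of 0.5 to 0.8, and all dropout after week 12. Because the remedy uses values already scheduled and loses no precision under MCAR, the change is worth making even though the bias may prove small.

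**What to change.** - **Summary and 8.2:** state MAR in both.
- **8.3:** remove the week-24 HbA1c requirement from the FAS. Without this edit a new model has no missing week-24 value to recover.
- **8.4.1:** make the primary model a repeated-measures model on HbA1c change at weeks 12 and 24, with treatment by visit, baseline HbA1c by visit, unstructured covariance, and the week-24 treatment contrast as the primary result. As an alternative, use multiple imputation by arm from week-12 HbA1c, followed by the planned ANCOVA.
- **8.4.1 with 5.1.1:** state how values after the start of antidiabetic therapy enter the model, so that the endpoint as defined is kept.
- **Sensitivity:** retain the complete-case ANCOVA.

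Cost: wording in four places, some programming and a slightly more complex primary model. Planned N stays at 392, with no new visits or samples. The change adds little for participants who leave before week 12.
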